Data for all measures will be collected directly from participants using an online survey administered at baseline and approximately six-months post-randomisation.

Additional research questions include:

- 1. **Delivery**: Can the STEER programme work under ideal circumstances?
- 2. **Impact**: a) What is the impact of STEER? b) For whom does STEER work and under what conditions?
- 3. **Unintended consequences**: a) Does STEER have any unintentional consequences? If so, what are these? b) Do different groups of young people experience these differently?
- 4. **latrogenic effects**: Are there any serious negative effects attributed to STEER on any intended or unintended outcomes?
- 5. **Mechanisms**: a) How does STEER work to reduce children and young people's involvement in serious youth violence? b) Which factors contribute most to the observed outcomes?

Design overview

The efficacy trial is a two-arm, parallel randomised control trial (RCT). All young people referred into the project, who meet the eligibility criteria and who consent to be part of the evaluation will be allocated at random to a treatment or control group on a 1:1 basis.

The table below presents an overview of the efficacy study trial design.

Figure 1 Summary of Efficacy Study design

Trial design, including number of arms	Two-arm parallel randomised controlled trial with random allocation at the young person level	
Unit of randomisation	Individual participant	
Stratification variables	Not applicable	

(if applicable)				
Primary outcome	variable	Reduction in prevalence and variety of self-reported offending behaviours		
	measure (instrument, scale, source)	SRDS Variety Score		
	variable(s)	A positive relationship between the young person and a significant adult (e.g., the mentor) Improved pro-social values and behaviours		
		Improved emotional symptoms		
		Improved behaviours		
Secondary outcome(s)		Positive relationships/role models		
		A positive relationship between the young person and a significant adult (e.g., the mentor) measured by the Social Support and Rejection Scale (SSRS) (Roffman et al. 2000)		
	measure(s)	Improved pro-social values and behaviours measured by the pro-social behaviour sub-scale in the Strengths and Difficulties Questionnaire (SDQ) (Goodman, 2005)		
	(instrument, scale, source)	Improved emotional symptoms measured by the SDQ emotional symptoms sub-scale (Goodman, 2005)		

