³ Please note that this rapid evidence assessment found that mentoring was more effective in reducing reoffending when contact between mentor and mentee was greater, in smaller scale studies, and when mentoring was combined with other services and interventions.

Figure 2: Sample size calculations

		Protocol	Randomisation
Minimum Detectable Effect Size (MDES)		0.19	0.186
Pre-test/ post-test correlations	Level 1 (participant)	0.0	0.5
	Level 2 (cluster)	N/A	N/A
Alpha		0.05	0.05
Power		0.8	0.8
One-sided or two-sided?		Two-sided	Two-sided
Number of participants by end of the trial	Intervention	327	337
	Control	327	349
	Total	654	686

Recruitment and baseline data collection was completed in October 2024. The cumulative T1 sample at the end of this period was 686.

337 young people were allocated to the intervention group, and 349 to the control group. This is broadly in line with the intended 1:1 allocation ratio. More information can be seen in Figure 3 below.

Referred into STEER = 1052 Eligible for STEER = Disengaged/became 997 ineligible= 316* Consented = Withdrew/excluded 694 from evaluation = 8 Baseline measures = 686 STEER= Signposting 337 = 349

Figure 3: Consort flow diagram for baseline data collection

Analysis

Overview

The following presents the analytical approach for the Efficacy Study. We currently do not know the structure of the complete data-set (for example, extent of or categories of missing data etc.) that we will receive as part of the Efficacy Study. This should be considered when interpreting the following analytical plan.

There is considerable debate about best practice when it comes to the analysis of data from RCTs. For example, Twisk et al. (2018) advocate for utilising longitudinal analysis of covariance or a repeated measures analysis without the treatment variable, but with the interaction between treatment and time in the model controlled. They argue that failure to control for baseline differences in outcomes between the groups can lead to biased estimates in the treatment. Alternatively, others have cautioned against this approach (e.g., Sen, 2013).

Based on our understanding of the literature our analysis will be conducted using General Linear Models controlling for baseline measurement of the outcome variable. An intention to treat approach will be used with all models unless otherwise stated. This in line with YEF Guidance (YEF, 2021).

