We will be using a General Linear Model, repeated measures design (assuming normality) or a generalized linear model, repeated measures design if the SRDS Variety score is nonnormally distributed. We will include a treatment by outcome interaction term in the analysis.

This analysis is designed to evaluate the differences in SRDS Variety Score between those in STEER and those who received business as usual (i.e. the control group).

This analysis will be conducted in SPSS.

Secondary outcomes analysis

Our approach to analysis of secondary outcomes will mirror the approach outlined above for the analysis of the primary outcomes. The secondary outcomes are:

- A positive relationship between the young person and mentor measured by the Social Support and Rejection Scale (SSRS).
- Improved pro-social values and behaviours measured by the SDQ pro-social values subscale.
- Improved emotional symptoms measured by the SDQ emotional symptoms subscale.
- Improved behaviour measured by the SDQ conduct problems subscale.
- An increase in positive relationships/role models measured by the measured by the SDQ peer relationships problem subscale.

All SDQ subscales contain 5 items and are measured on scales from 0 to 10. For the prosocial values subscale high scores are desirable (e.g., greater prosocial values), but for the other subscales (e.g., emotional symptoms subscale, conduct problems subscale, peer relationship subscale) high scores are not desirable (e.g., greater emotional problems, greater conduct problems, poorer peer relationships).

The SSRS has 4 dimensions; 'Feels valued', 'Trust', 'Mentoring', and 'Negativity'. Each item is scored from 1 (never) to 5 (always). Each subscale score is the average of items that make up the subscale. Higher scores on the negativity scale reflect higher levels of stress and negativity within the relationship. For the overall scoring of the scale a high score represents a positive relationship.

We will be using general linear models, repeated measures design (assuming normality) or generalized linear models, repeated measures design if the particular subscale is non-normally distributed. This will be determined once all data has been collected. We will include a treatment by outcome interaction term in the analysis.

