This analysis is designed to evaluate the differences in prosocial values, emotional symptoms, behaviour, peer relationships and positive relationships between the young person and mentor between those in STEER and those who receive business-as-usual.

This analysis will be conducted in SPSS.

Subgroup analyses

The subgroup analyses we will consider undertaking will be exploratory in nature. Before considering undertaking sub-group analyses we will assess whether these would be sufficiently powered based on the data we have collected. We will assess whether we are likely to have a sufficient number of young people in the groups by undertaking a power analysis after all data has been collected before proceeding with these analyses. We will explore the following analyses:

- Race equity, equality, diversity and inclusion. We will consider whether STEER was equally effective for those from minoritized backgrounds compared to those from White backgrounds. Given the limited knowledge about the effectiveness of interventions with those from minoritised backgrounds we would propose to conduct an exploratory analysis to consider whether the intervention was equally effective for those of Black (e.g., Black Caribbean/Black African) backgrounds to those of White backgrounds. This would likely be an underpowered analysis so caution would be taken interpreting the results.
- Reduced offending as measured by police data. If we are able to access the right kind of police data we will explore whether STEER had an impact on reducing offending over and above that reported in the business-as-usual group.

These analyses would be conducted using a general linear model, repeated measures design (assuming normality) or a generalized linear model. We will include a treatment by outcome interaction term in the analysis. As stated, we will only proceed with subgroup analyses where Power Calculations suggests the analyses will be sufficiently powered.

Further analyses

We will evaluate the extent to which positive relationships between the young person and mentor (treatment group) or significant adult (control group) influenced the primary outcome over and above the impact of STEER through the SSRS.

We are proposing conducting this analysis because the theory of change suggests that a mechanism for STEER is that it has its effect through an increase in a positive relationship with a mentor.

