Analysis will be conducted using a General Linear Model, repeated measures design (assuming normality) or a Generalized Linear Model.

Interim analyses and stopping rules

As part of the pilot trial, we analysed the completeness, reliability and validity of outcomes questionnaires (including the measures of outcomes described above). We did this by conducting regular data quality audits including exploring: percentages of scale item completeness, scale means, standard deviations and skew as well as conducting Cronbach Alpha testing for scale reliability and correlation analysis to test theoretical validity. We will continue this approach for the duration of the Efficacy Study. Our interim analyses as part of the pilot trial did not, and will not, include a comparison between control group and treatment group data nor analyses of impact.

The trial will stop if Salford Foundation, YEF and Cordis Bright decide that STEER is unable to recruit a sufficient number of participants. Recruitment rates will be monitored against modelled targets regularly (monthly) and reviewed bi-monthly (at a minimum) as part of project group meetings. Any decision about stopping will be made in discussion with YEF and Salford Foundation colleagues.

The Salford Foundation project team will also be responsible for safeguarding of participants. They will report any serious adverse events overall and by trial arm. The trial will stop if Salford Foundation, YEF and Cordis Bright decide that STEER is unsafe for participants.

Longitudinal follow-up analyses

Other than assessing change in outcomes between baseline and follow-up as described above, there will be no other longitudinal follow-up analyses as part of the STEER evaluation.

Imbalance at baseline

We will produce a table of baseline descriptive characteristics for all young people before they were randomised and for those analysed. The baseline characteristics will include age, sex, ethnicity, and the relevant outcomes (SRDS Variety Score and SDQ subscales). We will report counts (including the numerator and denominator) and percentages in each category. Any differences will be discussed in the final evaluation report.

Missing data

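### The SSRS mechanism analysis is justified by mediation, but it describes only the SSRS–SRDS association given arm: no indirect effect is defined and nothing ties it to the planned arm comparison of SSRS

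*SAP*

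**What the plan says.** The item is in the SAP under Analysis, Further analyses. It opens "We will evaluate the extent to which positive relationships between the young person and mentor (treatment group) or significant adult (control group" and goes on to ask how far these relationships "influenced the primary outcome over and above the impact of STEER through the SSRS". The reason, drawn from the programme's theory, comes next: "a mechanism for STEER is that it has its effect through an increase in a positive relationship with a mentor". The method is one sentence: "Analysis will be conducted using a General Linear Model, repeated measures design (assuming normality) or a Generalized Linear Model". No mediator model, indirect effect, interval, confounder set or rule of interpretation is given.

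Three other places bear on it:

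- Secondary outcomes analysis lists "A positive relationship between the young person and mentor measured by the Social Support and Rejection Scale (SSRS") among the outcomes to be compared between arms.
- The Introduction asks, under mechanisms, "How does STEER work to reduce children and young people's involvement in serious youth violence".
- The Introduction also says that all measures come from a survey "administered at baseline and approximately six-months post-randomisation".

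**The concern.** A mechanism of this kind has two links: STEER changes the relationship, and the relationship changes offending. A model that judges SSRS beyond the effect of arm estimates only the second. Young people with better relationships may offend less in both arms whether or not STEER altered any relationship, so a clear SSRS coefficient is compatible with no mediation at all.

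SSRS is also not randomised. Part of its association with SRDS may come from shared causes. The only follow-up is the six-month survey, so the two are measured together and the direction between them is not established.

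At stake is the answer to the mechanism question. An association that is not an effect of STEER could be reported as support for the theory of change. The SAP says the syntax will be supplied only after data collection, so this wording is all the pre-specification this document gives.

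**Working it through.** **Inputs from the SAP.** "337 young people were allocated to the intervention group, and 349 to the control group" (Sample size calculations), 686 in total. Pre-post correlation of SRDS 0.5; two-sided alpha 0.05; power 0.80; MDES 0.186 (Figure 2).

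**Assumed inputs.** The SAP gives no SSRS–SRDS correlation. Partial correlations ρ of −0.10 to −0.30 are assumed, a better relationship going with less offending.

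**Step 1: the plan's own figure.** MDES = (t0.975 + t0.80) × √[(1 − r²) / (P(1 − P)N)], with N = 686, P = 337/686, r² = 0.25 and 683 degrees of freedom, gives 0.1856. The stated 0.186 reproduces, so the sample and correlation are used as stated.

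**Step 2: what each analysis estimates.** Let a be the effect of arm on SSRS and b the coefficient of SSRS in a model of follow-up SRDS on arm, baseline SRDS and SSRS.

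- Further analyses, as worded: b.
- Secondary outcomes analysis: a.
- The stated rationale: a × b, which neither section defines.

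**Step 3: no STEER effect on SSRS (a = 0, so a × b = 0).** Simulation of 3,000 trials per setting. Each pair of figures is for a causal SSRS effect, then for an association due only to an unmeasured common cause.

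| ρ | SSRS coefficient significant | Both links significant |
|---|---|---|
| −0.10 | 73.8%, 74.8% | 4.3%, 3.7% |
| −0.15 | 97.6%, 97.9% | 4.3%, 4.9% |
| −0.20 | 100%, 100% | 4.4%, 5.6% |
| −0.30 | 100%, 100% | 5.8%, 5.1% |

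Hand check at 0.10: Fisher z = 0.1003 × √(686 − 5) = 2.62. Then 2.62 − 1.96 = 0.66, and Φ(0.66) is about 0.745. The last column is close to 0.05 times the middle one, as expected when the arm test on SSRS is null: 0.05 × 0.74 = 0.037 and 0.05 × 1.00 = 0.05.

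With an assumed 20% attrition (270 and 279), the SSRS coefficient is significant in about 65–67%, 94–95%, 100% and 100% of trials, and both links in 3–5%.

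**Step 4: mediation present.** With a = 0.4 SD and a causal ρ = −0.20, both links are significant in 99.9% of trials. The mean indirect effect is −0.069, against 0.4 × (−0.20) × √0.75 = −0.069. Requiring both links does not stop a real mechanism of that size from being seen.

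**Step 5: limits of the product.** Suppose STEER raises SSRS by 0.5 SD, neither STEER nor SSRS affects SRDS, and a shared cause gives ρ = −0.20. The product then averages 0.5 × (−0.20) × √0.75 = −0.087 SD when the truth is 0. The SSRS-adjusted arm coefficient shifts by the same amount, to +0.087 SD. Mediation arithmetic alone therefore gives no protection against unmeasured confounding.

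**The case against.** The strongest reply is that the first link is already planned. If STEER left relationships unchanged, the secondary SSRS comparison would be null in about 95% of trials, and a careful reader of the report would see it. Read together, the two planned tests amount to the joint check in the last column of the table. This stands, and it limits the point: what is missing is the connection between the two results and a defined indirect effect. Nothing in the SAP requires them to be read together.

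Three stronger readings are tempting, and the SAP supports none of them.

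- A reader might infer that a significant SSRS coefficient would be taken to confirm the theory of change. The SAP sets no decision rule and does not say that this model alone answers the mechanism question.
- A reader might take 74% to 100% as a false-positive rate. It is the power to detect an association built into the simulation, not the error rate of any claim the SAP makes.
- A reader might infer that the SSRS-adjusted arm coefficient would be reported as impact. The Analysis overview estimates the arm difference from a model with the baseline outcome and treatment only.

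The sentence is also ambiguous, because its last words may mean only that the relationship is measured by the SSRS. On either reading no indirect effect is defined. Finally, the simulation uses a single-outcome regression, while the SAP's first option is a repeated measures model that does not say how SSRS enters.

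**Conclusion.** The point holds as a mismatch between rationale and analysis. The item is motivated by an effect through the relationship, but it describes the SSRS–SRDS association given arm. If STEER does not change SSRS and the partial correlation is 0.10 to 0.20 in size, that association is significant in about 74% to 100% of trials, against about 5% for both links together. These figures rest on the assumed correlations, on complete follow-up of 686 (somewhat lower with 20% attrition), and on the regression form used here. They show that the second link carries little information about the first.

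This is a supplementary analysis, so no primary or secondary estimate depends on it. The change is still worth making before results are seen, because it is specific and uses data already planned.

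**What to change.** Replace the item with an exploratory mediation analysis:

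1. Take the arm effect on SSRS from the secondary analysis.
2. Fit six-month SRDS on arm, SSRS, baseline SRDS, age, sex, ethnicity and the baseline SDQ subscales, all of which the SAP already plans to report at baseline.
3. Report the indirect effect with a bootstrap interval.
4. Require a sensitivity analysis for unmeasured mediator–outcome confounding, because the product estimate is itself biased under it.

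Add three statements: no mechanism is claimed unless an arm effect on SSRS is also shown; SSRS and SRDS are measured at the same follow-up, so direction is not established; and the SSRS-adjusted arm coefficient is not the total impact of STEER.

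SSRS refers to a mentor in one arm and a significant adult in the other. If it is judged not comparable between arms, report only the within-arm association and make no mechanism claim. The SAP should also say whether SSRS has a baseline value: the Introduction says all measures do, but the baseline entries in Figure 1 and the list under Imbalance at baseline omit it.

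The cost is a few sentences, one short extra analysis on data already planned, and a more cautious conclusion about mechanism.

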SAP version history	2
·	
Table of contents	3
Introduction	4
Design overview	5
Sample size calculations	7
Analysis	10
Analysis	10
References	17

Introduction

This is an efficacy study statistical analysis plan for a two-armed parallel randomised controlled trial (RCT) evaluation of Salford Foundation's STEER programme. The efficacy study included an internal pilot trial started in January 2022 which concluded in May 2023. The trial moved to a full efficacy study in August 2023 and is due to complete in May 2025.

Salford Foundation's STEER programme (STEER) is a six-month intensive mentoring, coaching, family support and case management programme. It pairs young people who are at risk of serious youth violence and child criminal exploitation with a youth worker (mentor). Participants take part in STEER on a voluntary basis. The mentor delivers weekly face-to-face sessions which follow a toolkit of mandatory and optional themed interventions. In addition to these sessions, STEER provides weekly wrap-around case work and support for young people and offers their parents/carers a total of 14 hours of family support to facilitate greater family cohesion.

The key research question of the efficacy study is:

"Does a co-designed mentoring, coaching, family support, and case management programme delivered to children and young people with known family members or peers involved in offending behaviour, reduce the likelihood of participant involvement in serious youth violence and future offending or reoffending in comparison to receiving business as usual?"

The key primary outcome measure for the evaluation will be a reduction in prevalence of self-reported offending behaviours measured by the Self-Reported Delinquency Scale variety scale.²

Secondary outcomes include:

 A positive relationship between the young person and a significant adult (e.g., the mentor)

• Improved pro-social values and behaviours (measured by the Strengths and Difficulties Questionnaire (SDQ) pro-social values subscale).

² For more information see here: https://res.cloudinary.com/yef/images/v1623145465/cdn/19.-YEF-SRDS-guidance.pdf

- Improved emotional symptoms (measured by the SDQ emotional symptoms subscale).
- Improved behaviours (measured by the SDQ conduct problems subscale).
- Positive relationships/role models (measured by the SDQ peer relationships problems subscale).

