[•] These are young people who disengaged or became ineligible because they: refused the service, had a parent who refused the service, moved out of area, were uncontactable, had too many services involved, or were deemed too complex due to an escalation in risk following the acceptance of referral.

The primary outcome for the evaluation of STEER is a reduction in prevalence of self-reported offending behaviours between baseline and six months as measured by the SRDS variety score.

The secondary outcomes that we are investigating are that young people receiving STEER compared to the business as usual (control) group have (See Figure 1 for more information about measures):

- A positive relationship with their mentor.
- Improved pro-social values and behaviours.
- Improved emotional symptoms.
- Improved behaviours
- Positive relationships/role models.

The General Linear Model will include the appropriate baseline outcome measure and the treatment dummy variable. For example, for the analysis of the primary outcome measure (SRDS Variety Score) the baseline SRDS variety score measure will be included and whether the individual received STEER or not

The purpose of these analyses is to estimate the difference between the STEER arm and the business-as-usual arm for each of the primary and secondary outcomes.

Variable transformation

It is possible that the baseline and outcome variables may be skewed. Skew will be assessed using the traditional criteria based on their distribution (i.e., skews of greater or equal to 1.0 or less than or equal to -1.0). Arguably, it is more desirable to use a generalised liner model (GLM) for the appropriate modelling of non-normally distributed variables (e.g., Akram et al., 2023), than it is to transform the data.

The analytic approach has been developed a priori and will be conducted with SPSS.

The syntax for all analysis will be provided once it has been developed after all data has been collected.

Primary outcome analysis

The primary outcome is a reduction in offending measured by the SRDS Variety Score. All young people will have completed the SRDS questionnaire before randomisation and again at around six months post-randomisation.

The SRDS Variety Score is measured on a scale from 0-19 with 0 indicating the young person has not reported any of the 19 forms of delinquency/offending behaviour and a score of 19 indicating that they have undertaken all forms of delinquency/offending behaviour.

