We will assess missing data before analysis. We will follow YEF guidance as appropriate and report on both: (1) the number of complete cases, and (2) the extent and pattern of missingness in the data. We will also attempt to establish the missing mechanism (i.e. what variables in the data are predictive of non-response). We will explore this through logistic regression models where the presence of missing data will be modelled with additional information that may be predictive of missingness. We will conduct this analysis in line with YEF guidance and will also discuss the types of missing data in the final report as per Table 1 and using the flow chart in Figure 2 in the YEF analysis guidance. For more information see:

https://res.cloudinary.com/yef/images/v1623145483/cdn/6.-YEF-Analysis-Guidance/6.-YEF-Analysis-Guidance.pdf Extent of and reasons for missing data will be assessed and summarised in the final report.

Unfortunately, there is no universally agreed approach to analysis in the event of item non-completion. In the event that a high proportion of cases would be excluded due to low rates of item non-completion (for example, if most participants miss a small number of items), our approach to missing data will balance considerations around data integrity with maximising statistical power. In this scenario, we would consider using statistical techniques to impute missing items. We will finalise and agree our approach to this for the final draft of the Statistical Analysis Plan in line with YEF guidance, i.e. once baseline data collection is complete and we have a greater understanding of the structure of the data.

Compliance

Overall compliance for the purposes of the efficacy study will be met when young people have been randomised and allocated into the treatment or control group. This is in line with the intention to treat approach specified in the YEF Statistical Analysis Guidance (YEF, 2021).

We will explore model compliance if Power Calculations suggests the analysis will be sufficiently powered. This will explore what level of dosage was associated with a desirable outcome on the SRDS. For example, does attending 75% of STEER mandatory sessions result in a similar impact as attending all sessions? This analysis will be conducted using a general linear model, repeated measures design (assuming normality) or a generalized linear model. We will include a treatment by outcome interaction term in the analysis.

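### The exploratory dosage analysis puts a causal question to non-randomised attendance, so a dose gradient could appear or be hidden whatever STEER's true effect

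*SAP*

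**What the plan says.** The main models are intention to treat (SAP, Analysis, Overview). The Compliance section counts a young person as compliant once randomised and allocated, then adds a second, conditional analysis: "We will explore model compliance if Power Calculations suggests the analysis will be sufficiently powered". Its aim is put first as an association: "This will explore what level of dosage was associated with a desirable outcome on the SRDS". The example that follows is causal: "does attending 75% of STEER mandatory sessions result in a similar impact as attending all sessions".

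The method is "This analysis will be conducted using a general linear model, repeated measures design (assuming normality) or a generalized linear model", with one further term: "We will include a treatment by outcome interaction term in the analysis". For the models in general, the Overview says: "The General Linear Model will include the appropriate baseline outcome measure and the treatment dummy variable". No predictor of attendance, instrument or warning about interpretation is given for the dosage analysis.

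Two other statements bear on it. In the Introduction: "Participants take part in STEER on a voluntary basis". In the Design overview, eligible and consenting young people are "allocated at random to a treatment or control group on a 1:1 basis". Randomisation therefore fixes arm and nothing else.

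**The concern.** The number of sessions attended is settled after allocation, by the young person and by circumstances. Those who complete every mandatory session may differ from those who stop in motivation, stability or risk. If such differences predict six-month SRDS beyond what baseline SRDS captures, a regression of SRDS on attendance mixes the effect of sessions with the kind of person who attends.

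Nothing in the planned model separates the two:

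- Baseline SRDS removes only the selection that runs through baseline SRDS.
- Controls have no STEER sessions, so an interaction with treatment does not show how would-be full attenders fare without the programme.
- The power condition guards against imprecision, not bias.

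The SAP promises caution over the underpowered comparison of Black and White young people, but makes no such statement here. At stake is a secondary conclusion about how much of the programme is needed, which bears on the SAP's own questions about the conditions under which STEER works and which factors contribute most.

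**Working it through.** **Inputs from the SAP (Sample size calculations).** 337 STEER and 349 control, total 686; pre-post correlation 0.5; two-sided alpha 0.05; power 0.80; stated MDES 0.186.

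**The plan's own figure.** MDES = M × √[(1 − R²)/(P(1 − P)n)], with R² = 0.5² = 0.25, P = 337/686 and M = t(0.975) + t(0.80) = 2.806 on 683 df. P(1 − P)n = 171.4, so MDES = 2.806 × √(0.75/171.4) = 0.1856. This reproduces 0.186 and serves only as a yardstick. The SAP gives no figure for the dosage analysis.

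**Assumptions that are not in the SAP.** STEER has no effect. Engagement is a standard normal trait, unrelated to baseline SRDS. The more engaged half of the STEER arm attends everything. Given baseline, engagement has correlation −c with six-month SRDS. Both c and the 50% split are assumed.

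**Full against other attenders within the STEER arm.** The two halves differ by 2√(2/π) = 1.596 SD in mean engagement. The baseline-adjusted residual SD is √0.75 = 0.866. So:

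- gap = −c × 0.866 × 1.596
- SE ≈ 0.866 × 2/√337 = 0.094

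At c = 0.2 the gap is −0.276. The residual SD shrinks slightly, so the SE is 0.093, the ratio is 2.97, and about 84% of null trials are significant.

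| Residual correlation | Gap within STEER arm (SD) | False positives | Full attenders vs controls (SD) | False positives |
|---|---|---|---|---|
| 0 | 0 | 5% | 0 | 5% |
| −0.05 | −0.07 | 11% | −0.03 | 7% |
| −0.10 | −0.14 | 31% | −0.07 | 14% |
| −0.15 | −0.21 | 60% | −0.10 | 25% |
| −0.20 | −0.28 | 84% | −0.14 | 40% |

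The last two columns use half the gap, with SE ≈ 0.866 × √(2/337 + 1/349) = 0.081. Simulated trials under these assumptions agree: 83% to 85% within arm and 40% to 42% against controls at −0.20. The comparison as randomised stays at 0.00 with about 5% rejections. With the sign of c reversed (higher-risk young people attending more), the bias at 0.2 is about +0.28 SD and could hide a benefit.

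**What an instrumental-variable analysis can and cannot do.** With arm as instrument, the estimate is the intention-to-treat effect divided by the between-arm difference in mean exposure. The intention-to-treat SE is 0.866 × √(1/337 + 1/349) = 0.066. If a share p of the STEER arm attends any session and no control does, the SE becomes 0.066/p:

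- p = 80%: 0.083 (×1.25)
- p = 60%: 0.110 (×1.67)

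The choice of exposure matters. Suppose STEER truly lowers SRDS by 0.20 SD for full and partial attenders alike, half the arm attends everything, and the rest attend half the sessions (assumed).

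- Exposure *attended everything*: −0.20/0.5 = −0.40, double the truth.
- Exposure *share of sessions*, assumed linear: −0.20/(0.5 × 1 + 0.5 × 0.5) = −0.20/0.75 = −0.27.
- Exposure *any session*: −0.20/1 = −0.20, which is correct.

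**The case against.** The best defence is that this is a minor exploration. It runs only if judged sufficiently powered, its stated aim speaks of association, the causal phrase sits in one illustrative question, and every main model is intention to treat. All of that stands and limits the weight of the point. It does not remove it: the illustrative question is the only description of what the analysis is to answer, and the section carries no caveat.

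A second objection is that the bias is assumed. That is right as to size. With zero residual correlation there is none, at −0.05 it is small, and the direction could reverse. A reader might infer that a programme with no effect would show a benefit of more sessions. The SAP does not support that. It follows only if attendance is prognostic given baseline SRDS, and no attendance data are given.

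Third, the SAP does not define a comparison within the STEER arm, and the interaction term suggests that both arms are modelled. The larger figures in the table therefore cannot be called the planned result. The comparison with controls roughly halves the gap but does not remove it.

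Fourth, a reader might infer that the control arm could supply an unconfounded answer to the SAP's dosage question. It cannot without added assumptions: one binary instrument does not identify 75% against 100% attendance. Good instrumental-variable performance when the true effect is zero is no evidence to the contrary, because that test is then essentially the intention-to-treat test.

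**Conclusion.** The point holds in a conditional form. As written, the dosage analysis asks a causal question of a non-randomised, post-randomisation variable, with no safeguard against selection and no warning. If attendance predicts SRDS given baseline, a dose gradient can appear or be masked regardless of STEER's true effect. Under the stated assumptions the false gap within the STEER arm runs from nil to about −0.28 SD over residual correlations of 0 to −0.2, and passes the trial's MDES of 0.186 by −0.15. The actual size and sign cannot be known from the SAP. The primary intention-to-treat result is unaffected. The change is worth making because it is cheap, but the trial's main conclusion does not depend on it.

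**What to change.** In the Compliance section:

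1. Report SRDS by attendance band as descriptive only, state that the comparison is non-randomised, and remove the terms *result in* and *impact*.
2. If a causal estimate of receiving STEER is wanted, add a complier-average causal effect. Use two-stage least squares on all randomised young people with outcome data, arm as instrument, any STEER session attended as exposure, and adjustment for baseline SRDS. State the exclusion restriction: allocation affects SRDS only through attending STEER.
3. Say plainly that this does not identify the 75%-versus-100% contrast. A version using number of mandatory sessions (zero for controls) may be a sensitivity analysis, labelled as assuming a linear dose effect. Do not use a 75% or attend-all threshold as the exposure, since lower attendance may also have an effect.

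The cost is rewording and one standard model on attendance and outcome data that the dosage analysis already needs. The drawbacks are a wider interval (by 1/p, with p the share attending any session) and the loss of a causal answer to the dose-threshold question, which the planned model could not give either.
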